MECHANISMS OF WALKING RECOVERY AFTER STROKE (NCT02858349)

UNIVERSITY OF CINCINNATI IRB RESEARCH PROTOCOL 2016-1916

Most Recent IRB Approval: 2018-05-24

STUDY PROTOCOL AND STATISTICAL ANALYSIS PLAN

STUDY PROTOCOL

Research Design

[figure not shown]
This study will use a single-group repeated measures design. Ten subjects with chronic stroke will have clinical walking assessment and brain imaging before and after a 4 week control period and 4 weeks of locomotor high-intensity interval training (Figure 1). The control period will be used to confirm test-retest reliability of the measures and the absence of spontaneous improvements.^{1,2}

Recruitment. As in previous studies, we will recruit persons with stroke from the Greater Cincinnati Northern Kentucky area by collaborating with our large referral base of regional therapists, physicians and support groups and by using our existing database of >300 local persons with stroke who are interested in participating in research. Clinician referrals can be done in two ways: 1) the clinicians may provide our name and contact information to the potential subject; 2) if the potential subject verbally approves, the clinician can give us their name and contact information.

For persons interested in participating, we will further explain the study, confirm initial eligibility and perform informed consent. After a research staff member explains the purpose of study and the consent, potential participants will be given at least 24 hours to decide if they want to participate. During this consenting process, the subject will be provided a copy of the consent form. Standardized questions will be asked to ensure that the subject understands the study before consenting. The consent form also includes a HIPAA authorization.

Eligibility Criteria. Based on our research experience, previous studies and American College of Sports Medicine (ACSM) guidelines,³ we will observe the following eligibility criteria. **Inclusion criteria:** 1) age 30-90 years; 2) unilateral stroke experienced >6 months prior to enrollment in middle cerebral artery (MCA) territory without complete disruption of the putamen on the lesion side;⁴ 3) walking speed ≤ 1.0 m/s on the 10 meter walk test;^{5,6} 4) able to walk 10m over ground with assistive devices as needed and no physical assistance.⁷ **Exclusion criteria:** 1) MRI incompatibility (e.g. metallic or electronic implants, severe claustrophobia); 2) inability to perform mental imagery (time dependent motor imagery screening test [TDMI]);^{8,9} 3) evidence of significant arrhythmia or myocardial ischemia on treadmill ECG stress test, or significant baseline ECG abnormalities that would make an exercise ECG uninterpretable;³ 4) recent (<3 months) cardiopulmonary hospitalization; 5) unable to communicate with investigators or correctly answer consent comprehension questions; 6) significant ataxia or neglect (score of 2 on NIH stroke scale item 7 or 11);¹⁰ 7) severe lower extremity (LE) spasticity (Ashworth >2);¹¹ 8) recent (<3 months) illicit drug or alcohol abuse or significant mental illness; 9) major post-stroke depression (PHQ-9 ≥ 10)¹² in the absence of management of the depression by a health care provider (either anti-depressant medication or psychotherapy); 10) participating in physical therapy or another interventional research study; 11) recent (<3 months) paretic LE botulinum toxin injection; 12) concurrent progressive neurologic disorder or other major medical, orthopedic or peripheral vascular conditions that would limit improvement; 13) pregnancy.

Screening. After informed consent, subjects will undergo a screen including: medical record review, a history and physical, a depression screen (PHQ-9),¹² stroke-specific testing of mental imagery ability (TDMI),^{8,9} aphasia screening (Western Aphasia Battery Screening Test¹³), a motor impairment assessment (Fugl-

Meyer¹⁴), a 10m walk test,^{5,15} a resting ECG, a treadmill screening test¹⁵ and a stroke-specific treadmill ECG stress test¹⁶ to confirm eligibility and to obtain baseline characteristics and potential cofactors.

Stress testing will be performed, according to published guidelines,^{3,17,18} by the trained, experienced clinical staff of the University Hospital Cardiovascular Stress Laboratory (UH-CSL), with assistance from a licensed physical therapist on the study team. Subjects will wear a harness secured to an overhead support system for safety in case of loss of balance (not for body weight support). ECG and vitals will be monitored according to published guidelines.^{3,17,18} Subjects will perform a peak effort, graded treadmill stress test to volitional fatigue, individualized based on the treadmill screening test.¹⁶ Test termination criteria will include subject request to stop at volitional fatigue, severe gait instability, or according to published guidelines.^{3,16-18} This initial stress test will be conducted without oxygen uptake (VO₂) measurement to maximize subject communication and comfort.⁷

Subjects will be notified about the results of their ECG and stress test. If they are disqualified from further participation in the study based on the results of these tests, they will also be given the option to have the results sent to their physician.

Women of childbearing potential will be asked if there is any possibility that they are pregnant before any study activities take place. As part of the informed consent process, these participants will also be instructed to notify the research staff if the possibility of pregnancy arises at any point while enrolled in the study. In the case of possible pregnancy, study activities will continue only after a urine pregnancy test is done and found to be negative.

The Locomotor HIT Intervention was developed in our pilot work. Subjects will train 45 minutes, 3 times per week for 4 weeks. A harness connected to an overhead support system will be used for fall protection (not weight support) during all treadmill walking and subjects will be closely guarded by a licensed therapist at all times. Each training session will consist of a 3 minute warm up (30-50% HR reserve), 10 minutes of floor HIT, 20 minutes of treadmill HIT, 10 more minutes of floor HIT and a 2 minute cool down. HIT will involve repeated bursts of walking at maximum safe speed, alternated with recovery periods. During each session, treadmill speed will be systematically progressed based on performance. During floor HIT, subjects will be given visual feedback about the distance covered during previous bursts and encouragement to increase distance with each burst. One or more activity monitor(s) (see clinical Outcome Testing below) and a heart rate monitor will be worn during training sessions to characterize and monitor training intensity.

Clinical Outcome Testing will be done before and after the 4 week control period, then again after the locomotor HIT intervention. This testing will be conducted by a licensed physical therapist, with assistance from a research assistant as needed. Each outcome testing session will last approximately 2 hours and may include the following measures:

Walking speed is the gold standard measure of post-stroke walking function that reflects overall mobility¹⁹⁻²¹ and health status.²² It is reliable and valid after stroke.^{23,24} Walking speed will be captured with a stopwatch and/or with the GaitRITE, a commercially available 14-ft electronic walkway with 16,128 embedded pressure sensors, which instantaneously processes walking trial data to reliably and validly compute temporal-spatial gait parameters, including walking speed.^{25,26} Participants will walk across the hallway and/or GaitRITE, using assistive devices, orthotics and guarding as needed. Each test may be performed twice at comfortable speed and twice as fast as safely possible. Comfortable walking speed will be the primary clinical outcome measure.

The *6-minute walk test* involves walking back and forth around two cones, using assistive devices, orthotics, guarding and rest breaks as needed.²⁷ The distance that the subject is able to walk in six minutes is recorded.

The NIH Toolbox Standing Balance Test involves holding up to 5 standing positions for 50 seconds each (<http://www.nihtoolbox.org/WhatAndWhy/Motor/Balance/Pages/Balance.aspx>). The sequence is: eyes

open on a solid surface, eyes closed on solid surface, eyes open on foam surface, eyes closed on foam surface, eyes open in tandem stance. Stopping rules are in place to ensure participant safety with these progressively demanding positions. Postural sway is recorded for each position using an accelerometer that the participant wears at waist level. Based on the postural sway during each attempted position, this test provides raw scores and age adjusted scores using national normative data. Elements of the *NIH Toolbox Cognition Battery* (<http://www.nihtoolbox.org/WhatAndWhy/Cognition/Pages/default.aspx>) may also be used.

The metabolic cost of gait is assessed using oxygen consumption rate (VO₂) measurement during quiet sitting followed by VO₂ measurement during treadmill walking at comfortable speed.²⁸ The metabolic cost of gait is the difference between VO₂ at comfortable walking speed and VO₂ at rest, normalized to walking speed.²⁸ VO₂ will be measured using the Parvomedics TrueOne 2400 metabolic cart²⁹ and a facemask interface. The metabolic cost of gait estimates the energy cost of daily mobility,⁷ increases with compensatory gait deviations,²⁸ and is reliable and valid after stroke.^{30,31}

Aerobic capacity testing uses a similar protocol to the stress test above. It involves a screening test to determine the fastest speed at which the person can safely walk followed by an individualized peak effort, graded treadmill exercise test to volitional fatigue with VO₂ measurement.¹⁶ For the peak effort test, treadmill speed will begin below the subject's individualized fastest safe speed. Increases in speed and/or grade will be used to gradually increase the workload to find each subject's peak exercise capacity.³ Test termination criteria will include subject request to stop at volitional fatigue, severe gait instability or according to published guidelines.^{3,16-18} Peak aerobic capacity is defined as the highest VO₂ measurement achieved during the test. After finishing this test and a rest period, subjects may complete a verification phase to determine whether maximum physiologic capacity (a true VO₂-max) was reached.³² During this verification phase, the subject will be asked to walk as fast as possible for approximately 3 minutes. VO₂ data will be examined for a plateau, which would indicate VO₂-max.³²

Daily physical activity assessment involves wearing an activity monitor continuously during waking hours for ≥3 days and recording sleep/wake times.³³⁻³⁶ The monitor(s) will be worn around the non-paretic ankle and/or on the wrist or in a pocket. This monitoring records the number of steps taken and patterns of walking activity, and uploads data to computer software for analysis.

The *Kinesthetic and Visual Imagery Questionnaire (KVIQ-10)* involves having the participant perform 5 different movements followed by mental imagery of each movement. The participant is asked to rate the clarity of the visual imagery and the intensity of the imagined sensations for each movement on separate 5 point scales. The KVIQ-10 has been shown to be reliable and valid for persons with stroke.³⁷

The *Stroke and Aphasia Quality of Life Scale* is a reliable and valid self-report quantitative survey that includes up to 53 questions about quality of life related to stroke and was designed to maximize response feasibility for persons with and without aphasia.^{38,39}

*The Global Rating of Change (GROC)*⁴⁰ is a questionnaire that assesses overall impressions of change in health status from the perspective of the participant. The GROC is a 15 point ordinal scale with -7 indicating "a very great deal worse," 0 indicating "no change," and +7 indicating "a very great deal better". The GROC is not applicable at baseline testing because it measures change only.

Brain Imaging Procedures

Like clinical outcomes, brain imaging will be performed before and after the 4-week control period and after the locomotor HIT intervention for subjects with stroke. All scans will be performed on a 3.0T MRI system in the Imaging Research Center at CCHMC. Each imaging session will involve approximately one hour of brain scanning. During scanning, subjects will be positioned in a custom scaffold to stabilize the body and control leg movement. Initial alignment scans will be performed, followed by high-resolution anatomical scans, diffusion scans, functional scans and perfusion scans. The functional scans will be focused on the assessment of brain activation during imagined walking,^{41,42} knee extension^{43,44} and cognitive tasks. These tasks may involve

presentation of visual or auditory stimuli and subjects may be asked to respond by performing an actual or imagined movement, a cognitive task or by button-press. Subjects will be monitored by camera during functional scanning for compliance. Subjects will also practice task conditions prior to brain imaging.

Adverse Event (AE) Monitoring

Each study visit, subject voluntary reporting of AEs will be encouraged and AEs of interest will be specifically queried for subjects with stroke, including: falls, orthopedic injuries, faintness, new/increased pain and muscle soreness. During clinical testing and training sessions, subjects will also have monitoring and post-session questioning to identify any signs or symptoms of cardiorespiratory insufficiency, new/worsening neurological impairments or orthopedic injury.

STATISTICAL ANALYSIS PLAN

Clinical Trial Hypotheses. From PRE-2 to POST, subjects will exhibit a significant increase in walking speed (primary hypothesis) and other outcomes (secondary hypotheses).

Statistical Analysis. A mixed effects general linear model will be used with the outcome of interest (e.g. walking speed) as the dependent variable, a fixed (categorical) effect for time (PRE-1, PRE-2, POST) and an unstructured covariance matrix to account for repeated measures within the same participant. Hypotheses will be tested by the significance of the contrast estimate from PRE-2 to POST at the 0.05 significance level. PRE-1 and PRE-2 will also be compared to confirm test-retest reliability and the absence of spontaneous changes during the control period.

LITERATURE CITED

3. American College of Sports Medicine (ACSM). *ACSM's guidelines for exercise testing and prescription*. 9th ed. Philadelphia, PA: Lippincott Williams & Wilkins; 2014.
11. Ashworth B. Preliminary trial of carisoprodol in multiple sclerosis. *Practitioner*. 1964;192:540-542.

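### Does leaving open the instrument, course and choice of pass for comfortable walking speed undermine the primary PRE-2 to POST contrast?

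*Combined protocol and SAP*

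**What the plan says.** The pace of the primary outcome is fixed in Clinical Outcome Testing: "Comfortable walking speed will be the primary clinical outcome measure". Its measurement is left more open. On the instrument: "Walking speed will be captured with a stopwatch and/or with the GaitRITE, a commercially available 14-ft electronic walkway". On the course: "Participants will walk across the hallway and/or GaitRITE, using assistive devices, orthotics and guarding as needed". On repetition: "Each test may be performed twice at comfortable speed and twice as fast as safely possible". No hallway length is given, and nothing says whether two passes are averaged or one is chosen. The only named walking-speed course is in Eligibility Criteria, "walking speed ≤ 1.0 m/s on the 10 meter walk test", and it is not tied to the outcome.

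The SAP's Statistical Analysis section fits a mixed model with time as its only fixed effect and an unstructured covariance. The test is stated as "Hypotheses will be tested by the significance of the contrast estimate from PRE-2 to POST at the 0.05 significance level". The control period is used as follows: "PRE-1 and PRE-2 will also be compared to confirm test-retest reliability and the absence of spontaneous changes during the control period". The model has no term for measurement method.

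**The concern.** Research Design describes ten participants and no concurrent control group, so nothing outside the treated group could absorb a change in how speed is measured. If several participants were timed one way at PRE-2 and another way at POST, any systematic difference between the methods would enter the training contrast directly. It could create an improvement or hide one. The PRE-1 versus PRE-2 comparison is finished before such a change would occur and could not reveal it.

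A second route needs no switch. If both instruments are recorded at every visit and the reported one is picked after seeing the data, the primary test has two chances to succeed. Either course of action would comply with the text as written, and the outcome affected is the primary one.

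**Working it through.** The documents give no SD of change, no between-method difference and no power calculation, so there is no planned figure to reproduce. From the documents: n = 10, the PRE-2 to POST contrast, level 0.05. Assumed: two-sided testing, complete data (so that the contrast behaves as a paired t-test with 9 df, critical value 2.262), normal changes, and the offsets, SDs and correlations below. Partial-switch and choice results come from simulations of 1,000,000 trials per case.

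**1. Constant method.** Write the observed speed as true speed plus a method offset m. The observed change is then

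true change + (m at POST − m at PRE-2).

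With the same method at both visits the bracket is zero, whatever m is, and even if m differs between participants. The same holds if both instruments are used and averaged at every visit. It also holds on average for the rule on passes: the best of two exceeds the mean of two by within-session SD/√π, which is 0.011 to 0.028 m/s for an assumed SD of 0.02 to 0.05 m/s, but the excess is present at each visit and drops out. The type I error stays at 5.0%.

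**2. One-way switch after PRE-2, no true effect.** If k of 10 participants switch with offset b, the mean bias is (k/10) × b. For b = 0.05 m/s the bias is 0.005 m/s at k = 1, 0.015 at k = 3, 0.025 at k = 5 and 0.05 at k = 10. Two-sided rejection rates:

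| Switchers | b = 0.05, SD 0.10 | b = 0.03, SD 0.10 |
|---|---|---|
| 1 | 5.0% | – |
| 2 | 5.4% | – |
| 3 | 6.4% | 5.5% |
| 5 | 9.8% | 6.9% |
| 10 | 29% | 14% |

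With five switchers and b = 0.05 m/s, the rate is 12% at SD 0.08 and 7% at SD 0.15. The k = 10 column entries agree with the noncentral t: at SD 0.10 the noncentrality is (0.05/0.10) × √10 = 1.58, giving 0.293.

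**3. Switching without a preferred direction.** With five of ten switching, each at random up or down by 0.05 m/s (SD 0.10), the rejection rate is about 5.0%. The shifts add variance, which the paired SD picks up.

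**4. Opposite direction.** With a true gain of 0.10 m/s, SD 0.10 and b = −0.05, power falls from 80% to 65% (three switch), 53% (five) and 29% (all ten).

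**5. Choosing between two recorded values, no switch.** If either may be reported, the two-sided error is 7.3%, 8.0% and 8.6% at correlations of 0.9, 0.8 and 0.7 between the change scores. The hypothesis is an increase. Counting only false improvements, the rate is 3.6% at 0.9 and 4.0% at 0.8, against a nominal 2.5%.

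Steps 2 and 4 need a systematic difference between methods, a change after PRE-2, and a change running mainly one way. Step 5 needs both instruments recorded and a choice made after seeing the results. The documents describe neither set of conditions.

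**The case for a change.** The best argument for a change is that instrument and summary rule are part of the endpoint's definition. Without them a reader cannot confirm that the analysed value was fixed in advance. The design has no control group to cancel a drift in method, and the stability check looks at the wrong interval to find one. Describing the walkway as reliable and valid does not make it interchangeable with a stopwatch over a different distance. If staff would use one method anyway, writing it down costs little.

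Much of this stands. The text is silent, no other section fills the gap, and the one-way and choose-later scenarios do harm the test. The 5.0% for a single switcher also flatters slightly: in the same simulation its upward share is 3.3% rather than 2.5%.

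What does not stand is the step from silence to a flawed plan. The wording reads most naturally as equipment chosen once, or both pieces used each time, with a licensed physical therapist running the tests. Particular remedies are also choices among acceptable options. Requiring the walkway or the mean of two passes is a preference. Forbidding any substitution has its own price: losing one of ten pairs changes the 95% half-width from 2.262/√10 = 0.715 SD to 2.306/√9 = 0.769 SD, about 7% wider, whereas one substitution barely moves the error rate.

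**Conclusion.** No change to the plan is needed. The protocol omits operational detail about how comfortable walking speed is captured, but it states no rule that is wrong. Followed in either ordinary way, it gives an unbiased PRE-2 to POST contrast at the planned 5% level. Occasional or undirected switching leaves the two-sided error near 5.0%. The larger figures, 9.8% for five one-way switchers and 29% for all ten, rest on an assumed 0.05 m/s offset, an assumed 0.10 m/s SD of change and conduct that the documents do not plan. The 7.3% to 8.6% for choosing between two values likewise presumes selection after seeing the data. A competent analyst would take one instrument, one course and one summary of passes across the three visits and report which were used. The conclusion would differ only if study records showed that the method moved mainly one way after PRE-2, or that the reported value was selected on its result.

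### Does the SAP need a separate control-period analysis for the Global Rating of Change, which has no baseline value?

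*Combined protocol and SAP*

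**What the plan says.** Under Research Design the protocol states "This study will use a single-group repeated measures design", with ten participants, and gives the control period its purpose: "The control period will be used to confirm test-retest reliability of the measures and the absence of spontaneous improvements". Clinical Outcome Testing takes place before the control period, after it, and after training. These are the visits the SAP calls PRE-1, PRE-2 and POST. Each session "may include the following measures", and the GROC is on that list. It is a 15-point ordinal scale from -7 to +7, with 0 for no change, and it "assesses overall impressions of change in health status from the perspective of the participant". The same paragraph adds: "The GROC is not applicable at baseline testing because it measures change only".

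The SAP's Statistical Analysis section fits one mixed model to each outcome, with time as a three-level factor. It says "Hypotheses will be tested by the significance of the contrast estimate from PRE-2 to POST at the 0.05 significance level" and "PRE-1 and PRE-2 will also be compared to confirm test-retest reliability and the absence of spontaneous changes during the control period". Under Clinical Trial Hypotheses, walking speed is primary. The GROC is not named in the SAP and comes in only as one of the other, secondary outcomes.

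**The concern.** Read together, these statements seem to promise something the data cannot supply. The only control-period check is the PRE-1 to PRE-2 comparison. It needs a PRE-1 value, which the protocol says the GROC does not have, and the SAP neither exempts the GROC nor offers a substitute.

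There is a second difficulty. The model treats each outcome as a level to be differenced between visits, but a GROC rating is already a change. POST minus PRE-2 is then a difference between two change ratings, and its meaning depends on a reference point the documents do not give.

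With no parallel control group, the control period is the study's only comparison. A participant's own impression of change is the kind of measure that may move without any training effect. If the GROC escaped the check, a favourable rating at POST could be credited to training without any look at what participants reported when untrained.

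**Working it through.** The plan gives no figure on this point to reproduce. The check asks which comparisons the model can estimate, and what the surviving one means.

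**Inputs.** 10 participants (Research Design); time levels PRE-1, PRE-2, POST (SAP, Statistical Analysis); no GROC at baseline (Clinical Outcome Testing). Which sessions count as baseline is not defined, so both readings are taken.

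**Estimability.** Use one indicator column per visit and 10 rows per visit observed. A contrast is estimable if adding it as a row leaves the rank of the design matrix unchanged.

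| Visits with a rating | Rows | Rank | PRE-2 minus PRE-1 | POST minus PRE-2 |
|---|---|---|---|---|
| All three (e.g. walking speed) | 3 x 10 = 30 | 3 | estimable, 10 pairs | estimable |
| PRE-2 and POST (baseline is PRE-1 only) | 2 x 10 = 20 | 2 | not estimable, 0 pairs | estimable |
| POST only (baseline is both pre-training sessions) | 1 x 10 = 10 | 1 | not estimable | not estimable |

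The control-period comparison is unavailable for the GROC on either reading. The hypothesis contrast survives on the first reading, which is the more natural one, and not on the second.

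**Meaning of the surviving contrast.** Let c be the perceived change over the control period and h the perceived change over the training period.

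- Rated against the preceding visit: PRE-2 = c, POST = h, contrast = h - c.
- Rated against PRE-1: PRE-2 = c, POST about c + h, contrast about (c + h) - c = h.

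The two differ by h - (h - c) = c. As an illustration with c = +1 and h = +3, the contrasts are 3 - 1 = +2 and (1 + 3) - 1 = +3, and the PRE-2 rating is +1 in both. With c = 0 they coincide.

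This algebra assumes that perceived changes add up, which is only approximate on a bounded ordinal scale. It covers two reference points; with another one, the PRE-2 rating need not equal c.

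**What the analyst would do.** If PRE-2 and POST ratings exist, the model is fitted to those two visits, the planned contrast is reported, and the inapplicable comparison is left out. The reference period comes from the questionnaire, which may state it although these documents do not. Under the preceding-visit reading, the contrast already subtracts perceived control-period change. Under the PRE-1 reading, the PRE-2 rating shows that change directly. If only POST ratings exist, the model has no contrast to return, so the POST rating is simply described.

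**The case for a change.** The best case for amending the SAP is that the inconsistency lies in current text and would be cheap to mend. Two or three sentences could name the GROC visits, state the reference period, exempt the measure from the PRE-1 to PRE-2 comparison, and report the PRE-2 rating against 0. In a single-group study that rating would be a useful view of perceived change without training. Nor should c = 0 be assumed, since its absence is what the control period is there to confirm. A reader of these documents alone cannot tell whether the GROC contrast is h - c or h.

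Much of this stands. The comparison cannot be run, the rating visits and reference period are unstated, and test-retest reliability cannot be claimed for the GROC from this design. What does not follow is that a stated rule would produce a wrong answer. The proposed sentences would keep the planned contrast, record what the questionnaire may already say, and add a descriptive line for a measure the sessions need not include. That line also presumes a PRE-2 rating, which the documents do not confirm. Finally, the commitment to check the measures follows a sentence about walking assessment and brain imaging, so a promise covering the GROC is a possible reading, not an explicit one.

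**Conclusion.** The observation is correct, but no change to the plan follows. One comparison, for one optional secondary measure, is unavailable because of how the instrument works, and the protocol says so. A competent analyst would omit it without instruction. The hypothesis contrast remains estimable if the GROC is rated at PRE-2. Its two plausible meanings then differ only by c, the perceived control-period change. If the GROC is rated only at POST, the contrast is visibly absent, not wrong.

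This rests on two assumptions: that the questionnaire or study records show the reference period, and that nobody claims GROC reliability from the control period. The sample size, the 0.05 level and the primary walking-speed analysis do not depend on any of it.

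### Does predicting an increase in every secondary outcome put the wrong sign on metabolic cost of gait in a way that affects the analysis?

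*Combined protocol and SAP*

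**What the plan says.** The SAP has one hypothesis sentence, under Clinical Trial Hypotheses: "From PRE-2 to POST, subjects will exhibit a significant increase in walking speed (primary hypothesis) and other outcomes (secondary hypotheses"). It lists no secondary outcomes and gives no direction for any single outcome.

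The decision rule follows under Statistical Analysis: "Hypotheses will be tested by the significance of the contrast estimate from PRE-2 to POST at the 0.05 significance level". It does not say whether the test is one-sided or two-sided.

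The outcomes are described in the Study Protocol, under Clinical Outcome Testing. One is named as primary: "Comfortable walking speed will be the primary clinical outcome measure". The measures are introduced as optional: "Each outcome testing session will last approximately 2 hours and may include the following measures". Metabolic cost of gait is among them, with this definition: "The metabolic cost of gait is the difference between VO₂ at comfortable walking speed and VO₂ at rest, normalized to walking speed". The same paragraph adds that "The metabolic cost of gait estimates the energy cost of daily mobility" and that it "increases with compensatory gait deviations".

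**The concern.** In the hypothesis sentence, the predicted increase governs both walking speed and the other outcomes, without exception. For several listed measures an increase is an improvement: six-minute walk distance, peak VO₂, and the Global Rating of Change, whose positive end means better. Metabolic cost of gait runs the other way. The protocol calls it an energy cost and says it rises with compensatory gait, so a higher value is worse. No section says that increase stands for improvement or that any score is reversed.

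Taken at its word, the plan would count a significant worsening as support for this secondary hypothesis and a significant benefit as failure. Because sidedness is not stated, a directional sentence might also be turned into a one-sided test for an increase. Such a test would have almost no chance of detecting a true fall.

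**Working it through.** The plan gives no power, effect size or SD, so there is no figure of its own to reproduce. The check asks whether the predicted sign enters any quantity that the analysis produces.

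**1. Where the direction appears.**

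| Place | Direction stated? |
|---|---|
| SAP, Clinical Trial Hypotheses | Yes: an increase, for all outcomes |
| SAP, Statistical Analysis (decision rule) | No: significance of the contrast at 0.05 |
| Protocol, Clinical Outcome Testing, metabolic cost of gait | Implied: higher is worse |
| Success criterion for secondary outcomes | None defined |

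The sign is in the narrative and not in the rule.

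**2. Two-sided test.** With complete data on n = 10, the PRE-2 to POST contrast behaves as a paired t statistic, t = (mean change)/(SD of change/√10), on 9 degrees of freedom. The two-sided p-value is 2 × P(T₉ > |t|). It depends on |t| alone, so the predicted direction does not enter. The estimate and its confidence interval do not depend on it either.

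**3. One-sided test.** Take a true fall of d SDs of the change, with d assumed because the documents give no value. The noncentrality is −d√10, which is −1.58, −2.53 and −3.16 for d = 0.5, 0.8 and 1.0. The probabilities of a significant result at 0.05, from the noncentral t distribution on 9 df, are:

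| Test | d = 0.5 | d = 0.8 | d = 1.0 |
|---|---|---|---|
| Two-sided | 0.29 | 0.62 | 0.80 |
| One-sided for a decrease | 0.43 | 0.75 | 0.90 |
| One-sided for an increase | 0.0009 | 0.00003 | 0.000002 |

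The last row is the only route by which the word could do harm, and the plan does not prescribe that test. The row also shows no more than that a true fall seldom yields a significant rise, which holds for any outcome.

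**4. Does the definition set this measure against the primary hypothesis?** Cost = (VO₂ walking − VO₂ rest)/speed. If test speed rises by an assumed 10%, 20% or 30% and net VO₂ does not change, cost changes by 1/1.1 − 1 = −9%, 1/1.2 − 1 = −17% or 1/1.3 − 1 = −23%. Both conditions are assumptions. The protocol raises speed or grade to add workload in its aerobic capacity test, so constant net VO₂ at a faster speed is a favourable case. It also does not say whether the treadmill speed at POST is set afresh or held at the PRE value; if it is held, the divisor does not move. The arithmetic shows only that faster walking does not by itself imply a higher cost.

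**The case for a change.** The best case for a change is that a SAP exists to fix in advance what counts as confirming a hypothesis, and for this measure its only hypothesis sentence has the sign wrong. A two-sided p-value does not say whether a directional prediction was met; for that the predicted sign matters. Sidedness is unstated, no list of secondary outcomes excludes the measure, and the correction would take a few words.

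What stands is that the sentence is loosely worded and that, read literally, it does not suit metabolic cost of gait. The rest is weaker. The measure is one that sessions may include, and the SAP never names it as a secondary outcome, so the faulty hypothesis is inferred from a general phrase. The protocol's own description leaves no doubt which direction is good, and the title of reference 31, cited for this measure's reliability and validity, says that treadmill training reduces the energy expenditure of hemiparetic gait. A signed estimate would be read accordingly.

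The sidedness argument also cuts both ways. If contrasts are two-sided, the predicted sign has no effect on the test. If the plan did mean one-sided tests, declaring them two-sided would alter the primary test as well. By symmetry with the table, power for a gain in walking speed of 0.8 or 1.0 SD would go from 0.75 to 0.62, or from 0.90 to 0.80.

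**Conclusion.** No change follows. The hypothesis sentence uses increase as shorthand for improvement, and the shorthand fails for one optional measure. This is an editorial slip in the narrative and not an error in the decision rule. Writing improvement instead would alter no model, estimate, confidence interval or two-sided p-value, and the primary analysis of comfortable walking speed is untouched.

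This rests on two readings. The first is that contrasts are tested two-sided, the ordinary default where a plan is silent. The second is that analysts will judge metabolic cost of gait by the protocol's description of it, under which a fall is favourable. The power figures rest on assumed effects of 0.5 to 1.0 SD and complete data on ten participants. They show what a one-sided test for an increase would lose; they are not evidence of harm under the plan as written.
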